9. DATA COLLECTION

All data collection will be prospective and will be collected after the patient has voluntarily agreed to participate in the study by signing and dating an IRB-approved informed Consent and HIPAA document (as required by the local IRB). Data will be collected according to the scheme outlined in Table 1.

a. **Methods:**

- i. Data can be collected via paper form, or entered directly to an online database, if applicable.
- ii. If the site has an existing database, data may be sent to OrthoSensor via raw data format in an excel spreadsheet. If using a local database, it must be ensured that the data in the spreadsheet is compliant with the methods presented in the case report forms, as all data must be available for statistical analysis.

b. **Data and Clinical Assessments:**

- Patient Demographics: Age at surgery, gender, surgical side, height, weight, primary diagnosis. This data is collected from the medical record.
- Operative Data: Part Numbers (if able) or Femoral Component Type & size, Tibial Tray Type & Size, Tibial Bearing Type & Size, Patella Type & Size, OR Time, Surgical Technique, Surgical Approach, Operative Complications, Length of stay. This data is collected from the medical record.
- Length of stay, Discharge Destination: Based on the operation day and day of discharge, the length of hospital stay is determined.
- Patient Reported Outcome Measures – Perceived functioning, including pain, satisfaction and function will be measured using three patient reported outcome measures (PROMs).

- **EQ-5D**
A standardized instrument for use as a measure of health outcome
- **Knee Society Score (2011 Version)**

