The latest version of the KSS was developed in 2011 and introduced by the Knee Society. The latest version of the KSS originates from the popular KSS (from 1989); both physician and patient derived. It includes versions administered preoperatively and postoperatively. It has an initial assessment of demographic details, including an expanded Charnley functional classification. The objective knee score, completed by the surgeon, includes a VAS score of pain, walking on level ground and on stairs or inclines, as well as an assessment of alignment, ligament stability and ROM, along with deductions for flexion contracture or extension lag. Patients then record their satisfaction, functional activities, and expectations. Given the diverse activity profiles of many contemporary patients, the functional component of the score was improved to include a patient-specific survey, which evaluates features such as standard activities of daily living, patient-specific sports and recreational activities, patient satisfaction, and patient expectations. The new Knee Society Knee Scoring System has been developed and validated, in part, to better characterize the expectations, satisfaction, and physical activities of the younger and more diverse population of current patients undergoing TKA. The score was validated in a thoughtful and methodical fashion confirming internal reliability and analyzed for differential item functioning. The new Knee Society Scoring System is broadly applicable across sex, age, activity level, and implant type. Completing the questionnaire takes 10 to 30 minutes.
- **Forgotten Joint Score (FJS)**
The FJS is a patient reported outcome measure, consisting of 12 questions (e.g. awareness traveling in a car or climbing stairs?). It uses a 5-point Likert response format and the raw score is transformed to range from 0-100 points. High score indicates good outcome, e.g. a high degree of forgetting the joint in everyday life (forgotten joint phenomenon). The FJS has a low ceiling effect and was designed to discriminate between good, very good and excellent outcomes after TKA.
- **Knee Pain Evaluation Form**
The knee pain evaluation will be used to assess the prevalence and location site of knee pain when applicable. This evaluation will be completed by the investigator post total knee surgery during the intervals defined in Table 1 “Schedule of study assessments”.

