- Radiographic evaluation via Mediolateral and anteroposterior x-rays as is standard of care. The prevalence and location of radiolucency and/or osteolysis is evaluated on both AP and lateral views at each patient’s routine postoperative

follow-up visits. These evaluations are performed by each patient's operating surgeon.

- Complications, adverse events, and survivorship data will be collected and reported. This information will be gathered at each of the study follow-up visits.

c. Data Collection Periods:

Data will be collected pre-operatively, intra-operatively, and post-operatively at 6 weeks, 6 months, and 1 year. All time point windows are determined using the date of surgery (DOS) as day 0, including all annual visits. The visit windows are as follows:

Pre-operative: within 3 months prior to the date of the surgery excluding

*Pre-operative radiographs. Pre-operative radiographs taken within 12 months of scheduled knee replacement surgery are sufficient.

Intra-operative: within 2 weeks after the date of surgery

6 weeks: DOS + 6 weeks ± 4 weeks

6 months: DOS + 6 months ± 45 days

1 year: DOS + 1 year ± 90 days

2 year: DOS + 2 year ± 90 days

Table 1. Schedule of study assessments

Data Collected	Pre-op Baseline	Operative Discharge	6 Weeks	6 Months	1 Year	2 Years
Obtain Written Informed Consent	X					
Demographics	X					
Intra Operative		X				
EQ-5D	X		X	X	X	X
New-KSS	X		X	X	X	X
FJS			X	X	X	X
Knee Pain Evaluation Form				X	X	X
Radiographic Alignment	X		X	X	X	X
Adverse Event Reporting (When Present)		(X)	(X)	(X)	(X)	(X)

10. Analysis to be Performed on Data (e.g. Statistical Analysis)

Analysis of the data will be performed using SPSS version 21. Comparative Statistics will be run between outcomes data stratified by both groups: Analysis of variance (AVOVA) will be used to assess the difference between each group, with post-hoc t-tests to demonstrate significance. Separate analyses will be performed to evaluate power of sample sizes and any correlative affect that demographic/clinical variables may have on patient outcomes.

11. Monitoring of data collection

The Sponsor will monitor all data collected for accuracy and completion. The site will be monitored at least once per calendar year following the initial/first-monitoring visit.

12. Patient Identification

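### Section 10 names only mean-comparison methods, which do not suit the nominal outcomes (pain location, radiolucency location, discharge destination) or censored survivorship

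*Combined protocol and SAP*

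**What the plan says.** Section 10 of the protocol is the whole analysis plan. It opens the comparison of the groups with "Comparative Statistics will be run between outcomes data stratified by both groups" and then names the method: "Analysis of variance (AVOVA) will be used to assess the difference between each group, with post-hoc t-tests to demonstrate significance". The only other analyses it mentions are these: "Separate analyses will be performed to evaluate power of sample sizes and any correlative affect that demographic/clinical variables may have on patient outcomes". It makes no distinction by type of outcome. No chi-square, exact, logistic or time-to-event method appears anywhere in the document.

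Section 9b lists outcomes that are not scores:

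- Knee pain: "The knee pain evaluation will be used to assess the prevalence and location site of knee pain when applicable".
- Radiographs: "The prevalence and location of radiolucency and/or osteolysis is evaluated on both AP and lateral views". Section 3 repeats this among the study objectives.
- Hospital stay: "Length of stay, Discharge Destination".
- Safety and durability: "Complications, adverse events, and survivorship data will be collected and reported".

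Section 7.3 makes removal or revision of an implant an endpoint that ends follow-up. It also allows patients to withdraw at any time, and it foresees loss to follow-up and death.

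**The concern.** ANOVA and the t-test ask whether two means differ. Pain site, radiolucency site and discharge destination are unordered categories. Any mean of them is a mean of code numbers, and it changes when the categories are renumbered. Survivorship is time to revision, and some patients leave before 2 years. A t-test can be applied to it in two ways: as revised yes/no, which ignores when patients left, or as observed time, which confuses leaving the study with having a revision.

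An analyst who follows Section 10 for these outcomes therefore gets a result that depends on coding or on dropout. An analyst who sees the problem must choose another method with no rule fixed in advance. Knee pain is in the second objective and in the hypothesis (Section 3), and radiolucency location is also in Section 3, so some of the affected data bear on the stated aims.

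**Working it through.** **Inputs from the protocol.** 250 patients per group (Section 5); follow-up of 2 years (Section 2); method as in Section 10. The plan has no figure of its own to reproduce here: the 500 patients come with no alpha, power, effect size, event rate or dropout rate.

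**Assumptions, not in the protocol.** Two-sided alpha of 0.05; the four-category counts in step 1; 2-year revision of 4% in both arms; dropout between 5% and 25%; constant hazards of revision and dropout.

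**1. Nominal outcome.** Illustrative counts are 150/50/30/20 in one arm and 150/30/20/50 in the other.

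- *Chi-square.* Expected counts per arm are 150, 40, 25 and 35. The statistic is 2 × (0 + 10²/40 + 5²/25 + 15²/35) = 5 + 2 + 12.86 = 19.86 on 3 degrees of freedom, p = 0.0002. Renumbering the categories does not change it.
- *t-test.* With codes c1 to c4, the mean difference is (20·c2 + 10·c3 − 30·c4)/250.
 - Codes 3, 1, 4, 2: (20 + 40 − 60)/250 = 0, so p = 1.00.
 - Codes 2, 4, 3, 1: (80 + 30 − 30)/250 = 0.32, t = 4.05, p = 0.00006.
- Over all 24 numberings the mean difference runs from −0.32 to +0.32, and 10 of the 24 give p below 0.05.

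With two groups, ANOVA gives F = t², so it has the same fault.

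**2. Survivorship scored as revised yes/no.** With revision hazard λ and dropout hazard μ per year, the observed 2-year proportion is λ/(λ+μ) × [1 − exp(−2(λ+μ))].

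For 4% revision, λ = −ln(0.96)/2 = 0.0204. For 10% loss, μ = −ln(0.90)/2 = 0.0527. The proportion is 0.0204/0.0731 × (1 − 0.96 × 0.90) = 0.0380. Relative to the true 0.04 this is 0.949, about 5% too low. The ratio is 0.975 at 5% loss and 0.897 at 20%.

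**3. False positives when revision is equal in both arms.** 4,000 simulated trials per row:

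| Dropout by arm | t-test on observed time | t-test on revised yes/no | Log-rank |
|---|---|---|---|
| 10% / 10% | 4.8% | 4.6% | 4.5% |
| 5% / 15% | 79.8% | 5.0% | 5.0% |
| 5% / 25% | 99.8% | 6.2% | 5.2% |

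In the second row mean observed time is 22.9 versus 21.7 months. Dropout alone produces that gap of 1.2 months, and the t-test reads it as a difference between groups. The crude revision proportions in that row are 3.9% and 3.7%.

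**4. Plain yes/no outcomes.** Exact enumeration at 250 per arm gives the t-test on 0/1 data and Pearson chi-square the same type I error: 0.0499 at a 20% event rate, 0.0486 at 5% and 0.0455 at 1%. Power is also the same: 0.887 for 20% versus 10%, and 0.793 for 5% versus 1%.

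**The case against.** The strongest reply is that Section 10 does not say that every outcome will be tested this way. It refers to outcomes data without a list. Survivorship, complications and adverse events are only to be collected and reported, and discharge destination appears in no objective. This stands: a reader might infer that the plan commits to a t-test on survivorship, but the text does not say so. What it does show is that the only named method does not fit these outcomes and that nothing else is offered. Even a purely descriptive survival figure needs a method that handles censoring.

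A reader might also infer that mean comparisons of yes/no outcomes are meaningless. They are not. The mean of a 0/1 variable is the proportion, the mean difference is the risk difference, and step 4 shows no loss against chi-square. Nor do sparse counts reveal a special fault of the t-test: for 0/250 versus 4/250 the t-test and Pearson chi-square both give p = 0.045, and it is Fisher's exact test that differs, at p = 0.12.

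For the same reason, anterior knee pain recorded as present or absent is not coding-dependent. The problem arises only if all sites are placed in one numbered variable. The protocol does not describe the Knee Pain Evaluation Form in enough detail to tell how sites are recorded.

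Finally, the table in step 1 was constructed. It shows what can happen, not what to expect.

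**Conclusion.** The point holds for the nominal outcomes and for survivorship, and only for those. The single named method gives a coding-dependent answer for the former. For the latter, the damage depends on scoring and dropout: a t-test on observed time fails badly when dropout differs between arms, crude yes/no scoring has a small bias, and with equal dropout the false-positive rate stays near 5% either way. The sizes rest on the assumed counts, revision rate and dropout rates listed above. The dependence on coding does not rest on any rate.

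The continuous scores are unaffected. Yes/no outcomes (pain prevalence, radiolucency prevalence, complications) are not materially harmed at 250 per arm. What they lack is a stated effect measure with an interval and an exact method for sparse counts. It would also go too far to call survivorship the trial's main durability or harm outcome: Section 3 does not mention it, and Section 8 says the study is not meant to assess absolute product safety. The change is worth making because it is nearly free and removes a choice that would otherwise be made after the data are seen.

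**What to change.** Amend Section 10 to name the method by type of outcome:

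- **Continuous scores:** limit ANOVA and t-tests (linear models) to these.
- **Pain location, radiolucency or osteolysis location, discharge destination:** chi-square where each patient falls in exactly one category; otherwise a separate yes/no outcome per category, for example anterior knee pain present or absent.
- **Yes/no outcomes:** risk difference with 95% confidence interval, and an exact method when counts are sparse.
- **Survivorship:** Kaplan-Meier from the date of surgery with censoring at last contact, and a log-rank test if the groups are compared.

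The cost is a few lines of text. No extra patients, visits or data items are needed.

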Appendix I

Holding the Leg using Verasense

► **HOLDING THE LEG** For the correct depiction of intra-articular loading, in extension and flexion, the leg must be held with posterior support:

Step 1.

With the leg in extension, one hand is placed on the heel of the operative leg; one hand is placed under the backside of the knee, at the posterior capsule.

Step 3.

Soft tissues should continue to be evaluated at 45° (FIG A) and 90° of flexion (FIG B). If using a cruciate retaining component, an intraoperative posterior drawer test will allow the surgeon to assess PCL stability using the VERASENSE tracking option (FIG C).

Step 2.

Initial evaluation of soft tissue should always be assessed with the leg flexed in 10° with the posterior capsule relaxed and the screw home mechanism disengaged. Failure to do so could result in the over-releasing of soft-tissue, as loads tend to increase during terminal extension due to the screw home mechanism.

A

B

► HOLDING THE LEG (CONTINUED)

INCORRECT

Abducted/Externally Rotated

INCORRECT

Adducted/Internally Rotated

CORRECT

Neutral Position

Appendix II

Surgical Reference Guide

SURGICAL TECHNIQUE QUICK REFERENCE

Authored By: [name].
Holy Cross Hospital, Fort Lauderdale, FL

[figure not shown]
[name].
NYU Langone Medical Center, New York, NY

Assess soft-tissue load references with **joint reduced and capsule closed**. Only address soft-tissues after loads have been assessed in both **extension and flexion (10°-90°)**. After any tissue release, the **leg should be “cycled”** (taken through the range of motion) several times.

[figure not shown]
APPROACH TO VARUS KNEE

► TIGHT IN EXTENSION - MEDIALY

SENSOR PRESENTATION:

[figure not shown]

SURGICAL CONSIDERATION:

Evaluate MCL

Palpate fibers of MCL to assess tension. Release **posterior fibers of MCL** (both deep and superficial).

[figure not shown]

Evaluate Medial Posterior Capsule

Release medial posterior capsule and/or semimembranosus at tibial attachment site.

► TIGHT IN FLEXION - MEDIALY

SENSOR PRESENTATION:

[figure not shown]

SURGICAL CONSIDERATION:

Condition 1. Evaluate MCL

Palpate fibers of MCL to assess tension. Release **anterior fibers of MCL** (both deep and superficial).

SURGICAL CONSIDERATION:

[figure not shown]

Condition 2. Evaluate PCL

If medial femoral contact point exhibits excessive tension and posterior positioning, release **anterolateral bundle PCL fibers**.

► TIGHT IN FLEXION AND EXTENSION - MEDIALY

SENSOR PRESENTATION:

SURGICAL CONSIDERATION:

[figure not shown]
Condition 1. Loads 20-40 lbs. Extension Balancing:

- Posterior MCL fibers released if in tension; loads rechecked.
- Posterior medial capsule checked for tension and released, if needed; loads re-checked.
- If necessary, semimembranosus can be released.

Flexion Balancing:

- Anterior MCL fibers released if in tension; loads rechecked.

SENSOR PRESENTATION:

SURGICAL CONSIDERATION:

[figure not shown]
[figure not shown]
Condition 2. Loads > 40 lbs.

If loads beyond 40 lbs. are displayed, consider recutting the tibia plateau to add **additional varus alignment**.

[figure not shown]
 **ORTHOSENSOR®** Tel [name] [contact])
Training and Education [contact]

This document contains proprietary and confidential information belonging to OrthoSensor, Inc. Only trained medical personnel should use the OrthoSensor VERASENSE Knee System. OrthoSensor, as the manufacturer of the VERASENSE device, does not practice medicine and does not recommend any particular surgical technique or treatment for use on a specific patient. The surgeon who performs total knee arthroplasty is ultimately responsible for determining and utilizing the appropriate techniques for implanting the prosthesis in each individual patient.

[figure not shown]
[figure not shown]
APPROACH TO VALGUS KNEE

▶ **TIGHT IN EXTENSION - LATERALLY**
SENSOR PRESENTATION:

SURGICAL CONSIDERATION:

Evaluate Lateral Posterior Capsule & Arcuate

Palpate the lateral posterior capsule and/or the arcuate ligament to assess tension; release as necessary.

Evaluate IT Band

If lateral posterior capsule/arcuate does not fully address tension, consider releasing tight fibers of the IT band.

▶ **TIGHT IN FLEXION - LATERALLY**
SENSOR PRESENTATION:

SURGICAL CONSIDERATION:

Evaluate Popliteus

Release tight fibers of the popliteus tendon.

▶ **TIGHT IN FLEXION AND EXTENSION - LATERALLY**
SENSOR PRESENTATION:

[figure not shown]
SURGICAL CONSIDERATION:

Condition 1. Loads 20-40 lbs.
Extension Balancing:

- Release posterior lateral corner; recheck loads.
- Release posterior lateral capsule and arcuate complex; recheck loads.
- Consider releasing tight fibers of IT band, if necessary.

Flexion Balancing:

- If excessive loads are still uncorrected, then popliteus tendon is checked for tension and released.

[figure not shown]
SENSOR PRESENTATION:

SURGICAL CONSIDERATION:

Condition 2. Loads >40 lbs.

[figure not shown]
If necessary, you may recut tibial plateau to add more valgus.

TIGHT EXTENSION GAP

▶ **TIGHT ONLY IN EXTENSION - SYMMETRICALLY**
SENSOR PRESENTATION:

SURGICAL CONSIDERATION:

Condition 1. Loads 20-40 lbs.

Release posterior capsule.

[figure not shown]
SENSOR PRESENTATION:

SURGICAL CONSIDERATION:

Condition 2.

Loads >40 lbs.

[figure not shown]
If necessary, consider recutting distal femur.

ADVERSE FLEXION GAP

▶ **TIGHT ONLY IN FLEXION - SYMMETRICALLY**
SENSOR PRESENTATION:

SURGICAL CONSIDERATION:

Loads > 40 lbs.

Increase tibial slope.

▶ **LOOSE AND/OR UNSTABLE FLEXION GAP**
SENSOR PRESENTATION:

SURGICAL CONSIDERATION:

Loads < 10 lbs.

Increase thickness of shim.
